**LIST OF ABBREVIATIONS**

AE	Adverse Event
ANCOVA	Analysis of Covariance
ANOVA	Analysis of Variance
CI	Confidence Interval
CIP	Clinical Investigation Plan
CRO	Contract Research Organization
CTCAE	Common Terminology Criteria for Adverse Events
EC	European Community
ECOG	Eastern Cooperative Oncology Group
e-CRF	Electronic Case Report Form
g/m  h	grams per square meter per hour
Gy	Gray
ITA	Individual Typological Angle
ITT	Intention to treat
MASCC	Multinational Association for Supportive Care in Cancer
MedDRA	Medical Dictionary for Regulatory Activities
OR	Odds Ratio
PP	Per Protocol
PRO	Patient-Reported Outcome
PT	Preferred Term
RS	Reflectance Spectrometry
RT	Radiotherapy
RTOG	Radiation Therapy Oncology Group
SAP	Statistical Analysis Plan
SOC	Standard Of Care
SOC	System Organ Class
SOP	Standard Operating Procedure
TEWL	Trans Epidermal Water Loss

## 1. VERSION HISTORY

### 1.1 Version history of the SAP

Version Number	Summary/Reason for changes	Date issued
1.0	First version	18-Dec-2018

### 1.2 Version history of the Protocol

Version Number	Date	Description
1.0	06-02-2017	First version

### 1.3 Version history of the CRF

Version Number	Date	Description
1.0	30-Jun-2017	First version
1.1	25-Jul-2017	New fields creation, mandatory checks update

## 2. INTRODUCTION

### Justification for the design of the clinical investigation

Acute radiation dermatitis is a common side effect of radiotherapy in many forms of cancer, first of all breast and head & neck. The intensity of the reaction depends on radiotherapy parameters (dose per fraction, total dose, use of bolus or other beam-modifying devices, type and energy of radiation, size of the treatment field and site treated) and on concomitant chemotherapy employment. Although with a lesser grade, other factors involved in determining the intensity of radiation dermatitis are comorbidities (e.g. diabetes) and individual susceptibility.

Skin reactions during radiotherapy, scored according to different systems, usually span in severity from mild erythema (grade 1) to moist desquamation confined to skin folds (grade 2) or not (grade 3).

Large ulcerations that require surgical procedures (grade 4) with potential lethal consequences (grade 5) are exceptional and should be considered non-acceptable complications in routine practice.

Early onset of severe acute skin reaction during treatment could be responsible for a reduced compliance to the planned schedule of irradiation, so jeopardizing local disease control.

The most used scales for assessing toxicities (Radiation Therapy Oncology Group RTOG and CTCAE) do not capture symptoms as reported by the patients. Moreover, adverse events assessed by physicians are less accurate than patient-reported outcome (PRO) instruments and some clinicians have proposed replacing physician scales with patient-assessed reporting of adverse events.

A recent trial showed how CTCAE and the PRO Skindex-16 were supplementary and that patients reported a greater number of symptoms. The Skindex-16 allows patient rating of emotional and functional burdens that the CTCAE does not take into account. These adverse events cause patient's discomfort and impact negatively on quality of life. There is no gold-standard approach in the prevention and management of radiation dermatitis; however, a large variety of products and methods for the prevention of acute radiation-induced skin reactions have been tested, without identifying one product that has clearly demonstrated superiority over another.

Generally, preemptive treatments are aimed to reduce the drying effect of radiotherapy that causes desquamation and loss of the superficial protective layers of the skin. In this regard, the most employed agents are moisturizing creams, aimed at hydrating the skin and preventing the transcutaneous water loss.

Evidence-based recommended for practice include the employment of intensity-modulated radiation therapy and usual hygiene practices such as washing the irradiated skin and the use of mild soaps. The employment of a moisturizing cream based on urea or anionic polar phospholipid is advisable.

There is a strong need to study products with a preemptive role in radiation dermatitis development, with a trial design taking into account patient subjective evaluation and compliance.

#### Investigational device

Xonrid® is a promising EC-marked medical device for radiation dermatitis; it is a topical gel that prevents and treats skin symptoms such as erythema, itching, burning sensation and pruritus, induced by radiotherapy or other causes. When applied to the target skin areas, Xonrid® forms a protective film, reduces the TEWL (Trans Epidermal Water Loss) and increases moisturizing.

It promotes the healing process by restoring the physiological hydration levels of the affected skin areas.

It can be applied to the target areas including skin folds and creases, with or without minor trauma or abrasions.

Xonrid® is manufactured by Helsinn Healthcare SA.

In a recent pilot study using Xonrid®, the proportion of patients treated with Xonrid® and SOC preemptive treatment that not reached G2 radiation dermatitis at week 5 was 82.9%. Xonrid® use resulted associated with a decrease in the incidence of G3 toxicity and a delay in the development of G2 toxicity when compared to the data from a previous study (historical cohort). At week 5, patients with G2 and G3 dermatitis were about 52% and 10% in the historical cohort and 15% and 2% in the pilot study, respectively.

The aim of this clinical investigation is to evaluate if the use of Xonrid® in the prevention and treatment of G2 radiation dermatitis in breast and head & neck cancer patients can be a valid support, when compared to the Standard of Care as defined by MASCC (Multinational Association for Supportive Care in Cancer) guidelines.

Forty women affected by breast cancer and forty men and/or women affected by head & neck cancer, planned to undergo postoperative or curative radiation treatment have been enrolled in this clinical investigation.

### **3. STUDY OBJECTIVES**

#### **3.1 Primary Objectives**

The primary objective of this clinical investigation is to evaluate the proportion of patients without G2 radiation dermatitis at week 5.

#### **3.2 Secondary Objectives**

The secondary objectives of this clinical investigation are:

1. to evaluate the median time to G2 radiation dermatitis development according to CTCAE
2. to evaluate the proportion of patients without G2 radiation dermatitis at week 6 for both cancer sites, at week 7 for head & neck cancer and two weeks after the last radiation for both cancer sites .
3. to evaluate the worst skin toxicity during treatment and until 2 weeks after the last radiation, according to CTCAE
4. to evaluate changes in skin erythema and pigmentation and trans-epidermal water loss (TEWL)
5. to evaluate the mean and worst score of Patient Reported Outcome (PRO) with Skindex-16 questionnaire performed weekly
6. to evaluate the compliance to experimental treatment use
7. to evaluate the patient global satisfaction with treatment as assessed by Likert scale.

### **4. STUDY METHODS**

#### **4.1 Study Design**

This is a monocenter, open label, randomized, standard of care controlled, post-marketing clinical investigation.

#### **4.2 Treatment Administration**

Subjects have been randomly allocated to one of the following groups:

- Group A: Xonrid® gel + standard of care (SOC) preemptive treatment according to MASCC guidelines;
- Group B: standard of care (SOC) preemptive treatment according to MASCC guidelines.

Both Groups started treatment on the first day of radiotherapy and went on until two weeks after the last radiotherapy session.

Group B subjects received an additional standard treatment (according to Investigator's opinion) at G2 skin toxicity development.

All subjects interrupted the treatment and the study in the case of G3 skin toxicity development. This subjects have been treated according to the Investigator's opinion.

#### 4.3 Randomization and Blinding

The study was open label. Each patient for whom written consent was obtained have been assigned a five-digit screening code, consisting of the cancer area (e.g. 01 = head & neck; 02= breast) and a progressive number within the site: for example the first subject screened for head & neck cancer was assigned the code 01-001, the second one 01-002 etc.; the first subject screened for breast cancer was assigned the code 02-001, the second one 02-002 etc.

All screened subjects received the code irrespective of whether or not they were randomized. If a subject discontinued from the study at any time, the code was not re-used.

All subjects who signed the informed consent and received the screening code was entered into a Subject's Register, containing the name and surname of the patients and the date they have signed the consent form.

Eligible patients were randomized to receive the treatment according to a randomization list.

The patient randomization list was generated by Latis S.r.l., using the PROC PLAN of SAS 9.4 for Windows (SAS Institute Inc., Cary, NC, USA). Once eligibility of a patient was established (see Inclusion/Exclusion Criteria) the study treatment was assigned through centralized randomization system.

The Investigator also kept record of all enrolled patients in the Subject's Enrolment Log: the subject screening number, the date of consent, the treatment assigned to the patient, if applicable, or the reason for not being randomized were recorded.

### 5. STUDY ENDPOINTS

#### 5.1 Primary Endpoints

- Proportion of patients without G2 radiation dermatitis at week 5

#### 5.2 Secondary Endpoints

- Median time to G2 radiation dermatitis development according to CTCAE

- Proportion of patients without G2 radiation dermatitis at week 6 for both cancer sites, at week 7 for head & neck cancer and 2 weeks after the last radiation for both cancer sites.
- Worst skin toxicity during treatment and until 2 weeks after the last radiation, according to CTCAE
- Changes in skin erythema and pigmentation and trans-epidermal water loss (TEWL)
- Mean and worst score of Patient Reported Outcome (PRO) with Skindex-16 questionnaire performed weekly.
- Compliance to experimental treatment use
- Patient global satisfaction with treatment as assessed by Likert scale
- Study product safety and tolerability

### 5.3 Safety Endpoints

All randomized patients receiving at least a treatment dose have been included in the safety analysis.

Adverse events have been coded using the last updated version of the Medical Dictionary for Regulatory Activities (MedDRA) dictionary to give a preferred term (PT) and a system/organ class term (SOC) for each event. The number of patients who experienced at least one AE, study product-related AE, serious AE, severe AE and the number of patients withdrawn due to AE will be summarized by treatment arm.

For each SOC and preferred term, summaries will be made with respect to the proportion of patients having at least one occurrence of that event during the trial and the total number of events. The incidence of AEs in each treatment arm will be presented overall, by SOC and preferred term, and additional grouping by severity and relationship to the trial treatment. The comparisons will be analyzed using chi-square test.

## 6. PLANNED ANALYSIS

### 6.1 Interim Analysis

No interim analysis is planned.

### 6.2 Final Analysis

Final statistical analysis will be performed at the end of study, after database lock. Details of final statistical analysis are reported in the following paragraphs.

## 7. SAMPLE SIZE AND STATISTICAL POWER CONSIDERATION

In a previous observational study, 38.2% of the patients treated with SOC preemptive treatment according to MASCC guidelines did not reach G2 radiation dermatitis at week 5. In a pilot study using Xonrid®, the proportion of patients treated with Xonrid® and SOC preemptive treatment according to MASCC guidelines that did not reach G2 radiation dermatitis at week 5 was 82.9%.

According to these previous results, a two group chi-square test with a 0.05 two-sided significance level would have had 80% power to detect the difference between a proportion of patients that do not reach G2 of 38.2% in the Group B (standard of care (SOC) preemptive treatment according to MASCC guidelines) and a proportion of 82.9% in the Group A (Xonrid® and SOC preemptive treatment according to MASCC guidelines) when the sample size in each group is 18. To take into account a possible 10% dropout rate, 20 patients in each treatment group have been enrolled. As two cancer sites have been investigated, to assess the treatment effect within each site, 80 patients have been enrolled: 40 patients with breast cancer and 40 patients with head and neck cancer.

## 8. ANALYSIS POPULATIONS

### 8.1 Intent-to-Treat Population (ITT)

The study will be analyzed using an Intent-to-Treat (ITT) approach. All randomized patients receiving at least a treatment dose and having at least one post-randomization efficacy evaluation will be included in the ITT population for efficacy analysis. All randomized patients receiving at least a treatment dose will be included in the safety analysis.

### 8.2 Per-Protocol (PP) Population

Not applicable.

### 8.3 Safety Population

All randomized patients receiving at least a treatment dose will be included in the safety population.

## 9. GENERAL ISSUES FOR STATISTICAL ANALYSIS

### 9.1 Definitions, Derived Variables and Datasets

Analyses will be performed and report separately for each cancer site (i.e., breast cancer and head and neck cancer).

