6.4 Procedures

6.4.1 Study visits and assessments

Visit 1 screening (days from -3 to 0):

Subjects will be pre-selected on the basis of their medical history and the need of radiotherapy as curative or postoperative treatment for head & neck or breast cancer. Subjects will be evaluated with regard to the inclusion and exclusion criteria that will allow their participation into the study.

Before any study specific evaluation is carried out, subjects will receive all the information about the study by the Investigators and will sign an informed consent form.

The following assessments will be performed:

- Collection of information about demography
- Medical and surgical history
- Physical examination
- Concomitant medications and therapies
- ECOG performance status
- Erythema assessment
- Skindex-16 questionnaire
- Inclusion/exclusion criteria assessment

Visit 2 – randomization (Day1):

At visit 2 the subject eligibility will be re-assessed. Eligible patients will be randomized 1:1 in the two groups, treated respectively with Xonrid® + SOC or SOC alone.

The radiotherapy will start at this visit.

The following activities will be done at visit 2, before the first RT session:

- Inclusion/exclusion criteria assessment
- Randomization
- Physical examination
- Concomitant medications and therapies
- Erythema assessment
- Skindex-16 questionnaire
- Spettrophotometry examination and TEWL examination
- Treatment dispensation and instructions (the first application will be after RT session)
- Patient's diary dispensation and instructions on how to fill it in every day
- Adverse events recording

Visit 3 to 8/9 – RT and treatment:

Subjects will receive radiotherapy treatment every day for 6 or 7 consecutive weeks, with suspension only in the weekends. Breast cancer subjects are expected to attend 30 radiotherapy sessions (that means 6 weeks) while head & neck cancer subjects are expected to attend 33-35 radiotherapy sessions (that means about 7 weeks). One weekly visit for the study will be performed according to the subject availability (a ± 2 days window will be allowed and any delay will be recovered in the following visits).

The following activities will be done at visits:

- Physical examination
- Concomitant medications and therapies
- Erythema assessment
- Skindex-16 questionnaire
- Spettrophotometry examination and TEWL examination. Both exams will be done with clean skin, before the RT session

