7.3.6 Safety analysis

All randomized patients receiving at least a treatment dose will be included in the safety analysis.

Adverse events will be coded using the last updated version of the Medical Dictionary for Regulatory Activities (MedDRA) dictionary to give a preferred term (PT) and a system/organ class term (SOC) for each event. The number of patients who experienced at least one AE, study product-related AE, serious AE, severe AE and the number of patients withdrawn due to AE will be summarized by treatment arm.

For each SOC and preferred term, summaries will be made with respect to the proportion of patients having at least one occurrence of that event during the trial and the total number of events. The incidence of AEs in each treatment arm will be presented overall, by SOC and preferred term, and additional grouping by severity and relationship to the trial treatment. The comparisons will be analyzed using chi-square test.

Physical Examination data will be listed only, excepting baseline data, which will be summarized in terms of proportion of normal/abnormal findings.

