### **14.3 Safety data**

*Table 5.4.3.1.1. Analysis of adverse events observed among breast cancer patients*

*Table 5.4.3.1.2. Analysis of adverse events observed among breast cancer patients*

*Table 5.4.3.2.1 Analysis of adverse events observed among head and neck cancer patients*

*Table 5.4.3.2.2. Display of adverse events observed among head and neck cancer patients*

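### Adverse events are tabulated only within cancer site, so no planned output gives the rate, interval or between-arm comparison for the roughly 40 gel users together

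*SAP*

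**What the plan says.** SAP 9.1 sets the rule for the whole plan: "Analyses will be performed and report separately for each cancer site (i.e., breast cancer and head and neck cancer". SAP 14.3 applies it to safety. It lists four AE tables: two titled "Analysis of adverse events observed among breast cancer patients", one titled "Analysis of adverse events observed among head and neck cancer patients" and one titled "Display of adverse events observed among head and neck cancer patients". None covers all treated patients.

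The protocol is organised differently. Section 5.3 sets one safety and tolerability objective, for the study product. Section 7.2 defines one safety population, all randomised patients who received a dose, and SAP 8.3 repeats it. Protocol 7.3.6 summarises AEs by arm: "The incidence of AEs in each treatment arm will be presented overall, by SOC and preferred term". SAP 5.3, 11.5 and 12.2 also summarise by arm without mentioning cancer site. Protocol 7.3.3 limits subgroup analyses, if any, to exploratory use.

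SAP 13, which lists departures from the protocol, names only the dropped worst-toxicity analysis.

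**The concern.** The site split has a stated purpose for efficacy: Protocol 7.1 and SAP 7 size the trial so that the treatment effect can be assessed within each site. Neither document gives a reason for making it the only view of safety. The safety question concerns one gel, applied three times daily to irradiated skin in both sites.

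Under SAP 9.1 and 14.3, no planned output states how many of all gel-treated patients had a product-related, serious, severe or application-site AE, or withdrew because of one. No planned test compares the arms on these events in the whole safety population. A statement about the product's safety would rest on two tables of about 20 users each, or on an unplanned sum made by the reader.

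**Working it through.** **Inputs**

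- Enrolment, SAP 7: "80 patients have been enrolled: 40 patients with breast cancer and 40 patients with head and neck cancer".
- Arm size within a site, SAP 7: "To take into account a possible 10% dropout rate, 20 patients in each treatment group have been enrolled". Allocation, Protocol 6.4.1: "Eligible patients will be randomized 1:1 in the two groups". This gives about 20 gel users per site and 40 in all.
- AE rates: the documents give none. Those below are assumptions, shown as a range.

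**The plan's own figure.** For 38.2% v 82.9%, a two-sided 0.05 chi-square test with pooled variance and no continuity correction needs 18 per group. Power is 81.1% at 18 and 78.7% at 17. With 10% dropout, 18 / 0.9 = 20. The stated size reproduces.

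**Zero events among gel users.** One-sided 95% upper bound = 1 − 0.05^(1/n). Two-sided exact limit = 1 − 0.025^(1/n).

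| Gel users | One-sided 95% bound | Two-sided 95% limit |
|---|---|---|
| 20 (one site) | 13.9% | 16.8% |
| 40 (both sites) | 7.2% | 8.8% |
| 18 (one site, after dropout) | 15.3% | 18.5% |
| 36 (both sites, after dropout) | 8.0% | 9.7% |

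**One event in each site.** The site tables each show 1/20 (exact 95% CI 0.1% to 24.9%). The pooled figure is 2/40 (0.6% to 16.9%).

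**Between-arm comparison.** With d the difference in rates and p̄ their mean, power = Φ{[d√n − 1.96√(2p̄(1 − p̄))] / √(p₁(1 − p₁) + p₂(1 − p₂))}.

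For 5% on standard care v 25% on gel, d = 0.20, p̄ = 0.15, √(2 × 0.15 × 0.85) = 0.505 and the denominator is √0.235 = 0.485.

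- n = 20 per arm: (0.894 − 0.990) / 0.485 = −0.197, power 42%.
- n = 40 per arm: (1.265 − 0.990) / 0.485 = 0.568, power 71%.

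| Assumed rates, standard care v gel | 20 per arm | 40 per arm |
|---|---|---|
| 5% v 15% | 18% | 32% |
| 5% v 20% | 30% | 53% |
| 5% v 25% | 42% | 71% |
| 5% v 30% | 55% | 85% |
| 10% v 30% | 35% | 61% |

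Exact enumeration for 5% v 25% gives 44% and 76% for the chi-square test, and 30% and 65% for Fisher's test.

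**Chance of seeing a case at all.** At a true rate of 5%, one site table shows at least one case with probability 1 − 0.95^20 = 64%. Both tables are reported, so the chance that a case appears in at least one is 1 − (0.95^20)² = 1 − 0.95^40 = 87%, exactly the pooled figure. At 2% the corresponding values are 33% and 55%. The split therefore does not change the chance of observing an event. It changes only the precision and power of what is planned.

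**The case against.** A reader might infer that the split hides events or loses the sensitivity of 40 gel users. The documents do not support that. Every event falls in one of the site tables, SAP 16.1 plans AE listings, and the counts can be added. As shown above, the chance that a case appears somewhere in the planned output is unchanged.

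A reader might also take the word overall in Protocol 7.3.6 as a promise to pool sites. There it contrasts with summaries by system organ class and preferred term. The case for one all-patient summary rests on the by-arm wording in a single safety population. That is the natural reading, but it does not forbid site tables.

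Other objections stand in part:

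- **Exposure differs.** Protocol 6.2.1.2 gives 12–18 puffs per application in head and neck and 6 in breast. Section 6.2.1.1 supplies 12 v 4 bottles, and scheduled follow-up ends at day 63 v day 56. Section 6.3.1 accepts concurrent chemotherapy in head and neck only. A pooled rate averages two exposure levels and could understate risk at the higher one. This is a good reason to keep the site tables, but not to omit the pooled one.
- **No interval is planned.** SAP 12.2 plans counts and a chi-square test, so the upper bounds show what the data could support, not outputs that were removed.
- **Balance is assumed.** Neither Protocol 6.1 nor SAP 4.3 says that the randomisation list was stratified by site. A crude pooled comparison could mix site with arm.
- **Recording limits remain.** Protocol 14.3 keeps signs judged to be lack of efficacy out of the AE section unless they are serious or have another cause. Gel irritation could be recorded as dermatitis, so a tighter bound covers recorded AEs only.

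**Conclusion.** The point holds as a gap in planned reporting and as an undeclared narrowing of the protocol's safety summary. It is not a loss of data, and the primary efficacy analysis is unaffected.

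With 20 gel users per site and no dropout, pooling roughly halves the zero-event upper bound (13.9% to 7.2%). For an assumed 5% v 25% it raises chi-square power from 42% to 71%. The bounds depend only on the numbers treated. The power figures depend on assumed rates and, for the pooled case, on similar rates in the two sites.

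It would be wrong to conclude that pooling makes safety well powered: 5% v 15% reaches only 32%. It would also be wrong to conclude that site tables are inappropriate.

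**What to change.** 1. In SAP 9.1, exempt safety from the rule that analyses are done separately by site.
2. In SAP 12.2, 12.3 and 14.3, add one all-patient AE table by arm. It should cover any AE and product-related, serious, severe and application-site AEs, as well as withdrawals due to AEs.
3. Give an exact 95% CI for the gel-arm application-site rate, and a between-arm comparison stratified by cancer site, such as Mantel-Haenszel. Stratification protects against chance imbalance within site.
4. Keep the existing site tables, and note under the pooled table that gel amount, treatment duration and concurrent chemotherapy differ by site.
5. If safety is to stay split, declare and justify that in SAP 13.

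The cost is one extra table from data already collected, and no planned output is removed. The downside is a pooled rate that must be read beside the site tables.
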